**Clinical Study protocol: «Study of venous outflow from the lower limbs in patients with pelvic varicosities as a new strategy for compression treatment of pelvic varicose veins and varicose veins of the lower limb»**

**NCT:** no

**Date:** May 4, 2023

Compression therapy is basic treatment for chronic venous disease (CVD) of the lower limbs. Numerous studies have demonstrated the efficacy and safety of compression therapy in relieving symptoms such as pain, venous edema, leg heaviness and fatigue, as well as accelerating the healing of venous ulcers. It has been established that compression therapy is indicated for patients with both minimally expressed manifestations of CVD and severe forms of the disease. At the same only one study has been conducted to assess the correction of venous outflow from the lower limbs and pelvis in patients with pelvic varicose vein (PVV) and pelvic congestion syndrome (PCS). However, the incidence of this pathology ranges from 15 to 30% in the female population. The cost to the healthcare system of treating these patients in the United States exceeds \$2 billion. To date, the options and indications for compression therapy in patients with concomitant PVV and CVD have not been defined. The rational use of compression in this cohort of patients may contribute to the improvement of effective conservative treatment. In addition, inappropriate prescription of compression to patients with pelvic venous disease (which can be observed in real clinical practice) may discredit this simple, effective and safe therapeutic method. In addition, the research devoted to the problem of compression treatment of PVV will contribute to the development of new special compression products aimed at accelerating venous outflow from the pelvic organs. It can be assumed that this will serve as a stimulus for obtaining new data on the therapeutic effects of compression and create conditions for the creation of new technological directions in the production of compression knitwear.

**Aim: To study the venous outflow disturbance of the lower limbs in patients with PVV and to develop a new compression treatment strategy for patients with PVV and CVD.**

**Study goal:**

- To study the status of venous outflow from the lower limbs and pelvis in patients with concomitant PVV and CVD.;
- To identify correlations between the degree of impairment of venous outflow from the pelvis and the severity of impairment of the lower extremity musculo-venous pump (MVP) as the main peripheral determinant of venous return from the lower limbs.;
- To study the influence of the duration and extent (involvement in the pathological process) of pelvic venous reflux on the degree of venous outflow disturbance of the lower limbs;
- To develop ultrasound and radionuclide criteria for the severity of pelvic congestion syndrome;

- To study the possibility of using the coefficient of pelvic congestion syndrome (Cpcs) as a predictor of venous outflow disturbance of the lower limbs;
- To establish the criteria for correcting venous outflow disturbances in the lower limbs with compression based on the severity of pelvic congestion syndrome;
- To evaluate the effectiveness of compression therapy for CVD in patients with PVV (PCS) and impaired venous outflow from the lower extremities and the musculo-venous pump function.

## **Material and methods.**

This study enrolled 90 female patients, including 40 patients with PVV and PCS, 40 patients with combined PVV and CVD, and 10 patients with CVD without pelvic vein pathology.

### **Clinical study:**

All patients undergo examination by a physician-researcher who documents patient complaints, medical history, and physical examination findings in individual medical records. Chronic pelvic pain (CPP) and pain in the lower limbs will be assessed with a visual analog scale (VAS), which is a horizontal line 10 cm long, with each centimeter representing 1 point. The severity of pain on the VAS is estimated as follows: 0 points - no pain; 1-3 points - mild pain; 4-6 points - medium pain; 7-8 points - severe pain; 9-10 points - worst pain.

### **Diagnostics:**

Duplex ultrasound (DUS) of the lower limb veins will be performed on all patients. Transabdominal and transvaginal DUS will be performed on all 90 patients, too. Radionuclide venography of the left or right lower limbs (depending on the side of the lesion) will be also performed in all patients. Additionally, the single-photon emission computed tomography (SPECT) of the pelvic veins with *in vivo*-labelled red blood cells (RBCs) will be performed in all patients (n=90).

### **Treatments:**

Compression therapy with either class 1 or class 2 compression stockings will be administered to 90 patients with PVD and/or CVD. The selection of the compression class was based on the CEAP class and the severity of tibial MVP abnormalities according to radiophlebography data. The researcher will select the size of the compression product according to the standard scheme after verifying the diagnosis by pelvic and lower extremity vein DUS and radionuclide assessment of venous outflow from the pelvic and lower extremity veins (radionuclide venography and SPECT).

### **Rationale and basic information/ Abstract**

Currently, the term "varicose veins" implies not only the pathology of the superficial veins of the lower limbs, but also the pelvic veins. As yet, no epidemiological studies have investigated the frequency of the combination of pelvic and lower limb varicose veins, but in some studies the authors point to a combination of lower limb varicose veins and pelvic varicose veins (PVV) in 30-60% of patients. In this scenario, we are discussing the disease's clinically manifested forms, where lower limb varicose veins are visually identified and pelvic veins are identified by ultrasound and manifest as symptoms of pelvic congestion syndrome. There is no evidence of a concomitant occurrence of asymptomatic or latent forms of varicose veins in the lower limbs and PVV. (In these cases during duplex ultrasound angioscanning (DUS), pathological blood reflux is detected in the dilated superficial veins of the lower limbs and pelvis. However, there are no symptoms or signs of the disease.) As a result, it is not possible to assess the true prevalence of the combination of CVD and PVV.

At the same time, it is evident that dilatation and reflux in pelvic veins cannot but affect the clinical course of CVD in general and lower limb varicose vein disease in particular. Multiple studies from our clinic and foreign colleagues have substantiated this claim. It is caused not only by anatomical links between pelvic veins and lower limbs (perineal, clitoral perforating veins, tributaries of internal iliac veins), but also by common triggering mechanisms and similar pathogenesis of lower limb varicose vein disease and PVV.

Considering the above, valid questions arise about the effect of pelvic varicose veins with reflux on lower extremity venous outflow:

1. How does asymptomatic pelvic vein dilation with reflux impact venous outflow from the lower extremities and the clinical manifestations of CVD?
2. Does symptomatic pelvic vein dilation with reflux affect venous outflow from the lower limbs and clinical manifestations of CVD?
3. Does vulvar vein dilation affect venous outflow from the lower limbs and CVD clinical manifestations?
4. Is the severity or exposure of pelvic congestion syndrome a predictor for the development of lower limb venous outflow disorders?
5. How does the severity of clinical manifestations of PCS correspond to the severity of hemodynamic disturbance, as determined through instrumental research methods?

These questions have significance not only in academic and scientific domains. They are directly related to the strategy and tactics of treating patients with a combination of varicose veins of

lower limbs and PVV, PCS and CVD, since the following fundamental issues have not yet been resolved:

1. Do asymptomatic patients with instrumental detection of PVV and lower limb varicose vein require correction?
2. Is it appropriate to utilize compression knitwear in patients with an asymptomatic course of instrumentally confirmed venous outflow disorders with a combination of pelvic and lower extremity varicose veins?
3. Can the coefficient of pelvic venous congestion be utilized as a quantitative indicator to prescribe compression treatment for venous outflow disorders in the lower limbs of asymptomatic patients without signs of CVD? In other words, can the coefficient of pelvic venous congestion be used as a reference index for correcting the evacuative function of the tibial MVP in patients without clinical manifestations of CVD?
4. How effective is compression in correcting impaired venous outflow from the lower limbs in PVV patients?

The severity of the clinical course of lower limb CPV is determined by objective symptoms such as pain, edema, trophic disorders, and venous ulceration. In patients with CVD, the severity of the disease course determines the development of pelvic congestion syndrome (PCS), which is manifested by chronic pelvic pain (CPP), hypogastric heaviness, and dyspareunia. CPP and dyspareunia are the main indicators of the severity of the clinical course of PCS. It has been demonstrated that PCS exacerbates the symptoms of CVD. Thus, correlating the severity of pelvic pain to the degree of pelvic venous fullness (coefficient calculated by pelvic venous scintigraphy) allows us to assume the presence of venous outflow disorders of the lower extremities. According to this hypothesis, the presence and severity of venous outflow disorders of the lower limbs can be determined not only by the results of instrumental examination of the pelvic and limb veins, but also by clinical assessment of the severity of CPP.

### **Objectives of the study**

To examine the correlation between impaired venous outflow from the pelvis and venous outflow from the lower limbs, to identify predictors of impaired venous outflow from the lower limbs in patients with PVV without clinical manifestations of CVD, to determine indications for the use of compression therapy of the lower limbs in patients with PVV but without symptomatic CVD based on the severity of disturbances in venous outflow from the pelvis.

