### **Study design**

This is a single-center, prospective, comparative cohort study. The duration of the study is from 1/4/2023 to 1/12/2023. The study includes 90 patients (40 patients with symptomatic PVV without CVD, 40 patients with asymptomatic PVV and symptoms of CVD, 10 patients with lower limb varicose vein disease (CVD) without PVV).

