**Exclusion criteria:**

- Menopause;
- Pregnancy;
- Postthrombotic syndrome;
- Suspicion of May-Turner syndrome;
- Ultrasound signs of nutcracker syndrome.

Before being included in the study, every patient signs a voluntary informed consent form to participate in the research.

The study enrolled 90 female patients, including 80 patients with PVV and 10 patients with CVD without PVV. All patients undergo a physician examination and receive DUS of pelvic veins and lower limbs, regardless of the presence or absence of clinical manifestations of diseases of pelvic veins and lower limbs. Then the patients are classified into three groups based on clinical and ultrasound evaluation. The first group (n=40) comprises patients with symptomatic PVV, including pelvic pain, dyspareunia, and heaviness in the hypogastrium, but without symptoms or signs of CVD. The second group (n=40) consists of women with asymptomatic PVV but with indications of CVD. The third group consists of 10 patients with varicose veins in the lower limb, without PVV or PCS symptoms. All patients undergo radionuclide venography of the lower limbs and emission computed tomography (SPECT) of the pelvic veins with *in vivo* labelled red blood cells (RBC). Quantitative indicators of the function of the lower extremity muscle-venous pump (MVP) and the pelvic venous congestion syndrome coefficient (Cpvc) are objectively assessed, using the results of radionuclide venography and single-photon emission computed tomography (SPECT). These indicators include average radiopharmaceutical transport time from regions of interest, and objectively represent blood venous flow from the veins of the lower extremities and the pelvis. Compression treatment using class 1 or 2 stockings is prescribed for patients with impaired venous outflow from the lower limbs and impaired venous evacuation function of the lower leg vein duct, depending on the class of CVD according to CEAP. Follow-up examinations, including clinical evaluations and radionuclide studies with SPECT of the pelvic veins, are performed 10 days after the initial clinical examination and radionuclide phlebography to evaluate the efficacy of the compression treatment.

Radionuclide venography with single-photon emission computed tomography (SPECT) of the pelvic veins and repeated clinical examinations are performed to evaluate the efficacy of the compression treatment 10 days after the initial clinical examination. Figure 1 displays the study's design.

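### The compression-indication objective and the efficacy endpoint need a comparison with no compression, which the design does not contain

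*Protocol*

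**What the plan says.** Protocol, Objectives of the study, lists three aims: to correlate pelvic with leg outflow, to find predictors of impaired leg outflow, and "to determine indications for the use of compression therapy of the lower limbs in patients with PVV but without symptomatic CVD", the last "based on the severity of disturbances in venous outflow from the pelvis". Study goal has a matching item: "To establish the criteria for correcting venous outflow disturbances in the lower limbs with compression based on the severity of pelvic congestion syndrome". The third treatment question in the Rationale concerns women without clinical CVD and asks: "can the coefficient of pelvic venous congestion be used as a reference index for correcting the evacuative function of the tibial MVP". The Secondary endpoint covers the efficacy and comfort of class 1 and 2 stockings.

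On design, the protocol states: "This is a single-center, prospective, comparative cohort study". Its three groups are defined by disease. The one that matches the indication aim is group 1, "40 patients with symptomatic PVV without CVD".

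On who is treated, there are two statements:

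- Treatments: "Compression therapy with either class 1 or class 2 compression stockings will be administered to 90 patients with PVD and/or CVD".
- Study description under Exclusion criteria: "Compression treatment using class 1 or 2 stockings is prescribed for patients with impaired venous outflow from the lower limbs", with impaired calf-pump evacuation as a further condition.

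The study description and the Compression treatment item both judge efficacy by repeating the clinical and radionuclide examinations after 10 days. Follow-up adds two months of monitoring that also assesses efficacy.

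**The concern.** An indication says who should be given a treatment. To base it on pelvic congestion severity, one must know how outcomes with compression differ from outcomes without it, and how that difference changes with severity. An efficacy endpoint needs the first of these. The protocol follows women only while they are compressed, or leaves untreated only women who differ on the outcome, and it calls the resulting 10-day change efficacy.

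At stake is a causal conclusion that the data cannot carry. Publication ethics says that the results will feed methodological recommendations by the Ministry of Health, and the introduction itself warns that inappropriate prescription may discredit compression.

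**Working it through.** **Step 1: what each aim needs.**

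- Correlation of pelvic and leg outflow: baseline scans only.
- Predictors of impaired leg outflow, including Cpvc: baseline scans only.
- Primary endpoint (effect of PVV and PCS on leg outflow and pump function): no uncompressed course needed.
- Indications for compression by pelvic severity: outcome with and without compression, across levels of severity.
- Efficacy of stockings: outcome with and without compression.

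**Step 2: who could supply the course without compression.**

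- Treatments section: 40 + 40 + 10 = 90 women, all compressed. Nobody is untreated.
- Study description: stockings go to women with impaired outflow and impaired pump function. A woman left untreated lacks at least one of these impairments, so she differs from the treated women on the outcome variable. A woman with marked pelvic congestion but a normal pump would not be treated.
- Groups 2 and 3 against group 1: different disease, and also compressed under the Treatments section.
- Class 1 against class 2: class follows CEAP and pump impairment, so it is confounded with severity.

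None of these gives a comparable uncompressed woman. The two treatment statements contradict each other, but reconciling them either way does not change this result.

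**Step 3: what the 10-day change contains.** Observed change = compression effect + change that would have occurred anyway + measurement variation. One component can be illustrated. If women are selected because a baseline value lies above a cut-off c (in SD units of the unselected population), and the test-retest correlation is r, the expected fall with zero treatment effect is

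(1 − r) × φ(c) / (1 − Φ(c)) SD.

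The documents give neither r nor the position of the cut-off, so both are assumptions:

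| Cut-off | Share selected | φ/(1 − Φ) | Fall at r = 0.9 | Fall at r = 0.5 |
|---|---|---|---|---|
| −1 SD | 84% | 0.288 | 0.03 SD | 0.14 SD |
| mean | 50% | 0.798 | 0.08 SD | 0.40 SD |
| +1 SD | 16% | 1.525 | 0.15 SD | 0.76 SD |

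A simulation (3,000 studies, 40 selected women, paired t-test, no treatment effect) shows how often improvement would be declared falsely, against a nominal 2.5% in that direction:

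| Cut-off | r = 0.9 | r = 0.8 | r = 0.7 | r = 0.5 |
|---|---|---|---|---|
| mean | 19% | 37% | 49% | 77% |
| −1 SD | 5% | 8% | 10% | 14% |

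This applies to leg transport times if treatment follows the study description. If all 90 women are treated, selection on an abnormal leg scan disappears and this term shrinks. Group 1 is still recruited on pelvic symptoms, so its pain scores remain exposed.

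**Step 4: severity and change.** If the 10-day fall in Cpvc itself is related to baseline Cpvc, the expected slope with no treatment effect is (1 − r): 0.1 at r = 0.9 and 0.5 at r = 0.5. A larger fall in women with a higher baseline is therefore expected without any benefit.

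**The case against.** **Indication may be meant diagnostically.** The objectives run from correlation to predictors to indications, and the Rationale speaks of inferring leg outflow disorder from pelvic severity. On that reading Cpvc only marks women with an impaired pump, and no untreated arm is needed. This stands for the correlation and predictor aims. It does not cover the indication clause, which the protocol lists separately from predictors, while the Rationale asks separately how effective compression is in PVV. Nor can benefit be borrowed from CVD: the introduction says that indications in concomitant PVV and CVD are undefined, and group 1 has no symptoms or signs of CVD.

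**Cpvc is not named in the objective.** Correct. The objective speaks of pelvic outflow severity and the goal of PCS severity; the link to Cpvc comes from the Rationale. The point holds for any severity measure.

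**There is more than a 10-day change.** Also correct: Follow-up adds two months. It has no concurrent comparison either.

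**Expectation hardly affects isotope transport times.** Accepted. It is a concern for pain VAS; scan variation and regression to the mean remain for the scans.

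**A cohort study need not randomise.** A reader might infer that an uncompressed arm must be added. The documents do not support that: the design is declared a cohort and efficacy is secondary. Nor would splitting group 1 settle the question. At 20 versus 20, 80% power (two-sided 0.05) needs a difference of 2.80 × √(2/20) = 0.89 SD. For a compression-by-Cpvc interaction with 10 per cell it needs 2.80 × √(4/10) = 1.77 SD.

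**Conclusion.** The point holds for the indication clause in the Objectives, the matching criteria goal, the Rationale question on prescribing by the coefficient, and the efficacy endpoint. None can be answered as a claim against no compression under either statement of who is treated. This rests on reading indication and efficacy as claims of benefit, which the protocol's separate listing of predictors supports. The SAP is not shown, but no analysis plan can supply a comparison that the design leaves out.

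The size of the bias cannot be derived from the documents. The regression-to-the-mean figures rest on assumed r and cut-off and show only that the effect can range from slight to large.

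Two stronger readings are not supported. A reader might infer that the whole study fails its objectives; the cross-sectional aims and the primary endpoint need no untreated women and are unaffected. A reader might also infer that a Cpvc threshold derived from 10-day change will be published; no section says so. Publication ethics says only that study results will be used for recommendations.

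**What to change.** Change the wording in these places:

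- Study goal and Objectives: replace the criteria and indication items with the association between pelvic congestion severity (including Cpvc) and impairment of leg outflow and pump function.
- Secondary endpoint, the study description under Exclusion criteria, and the Compression treatment item: replace efficacy with the uncontrolled 10-day change under compression and its association with baseline Cpvc. Describe the two-month assessment in Follow-up in the same way.
- Add one statement, repeated in Publication ethics: no efficacy versus no compression, and no indication or prescribing threshold by Cpvc, will be concluded from this study or carried into the methodological recommendations.
- Reconcile the Treatments section with the study description on who receives compression. This is needed in any case and does not by itself close the gap.

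The cost is a less favourable claim. No patient, visit or scan is added.

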### **Primary endpoint of the study**

To investigate the impact of varicose veins of the pelvis and pelvic congestion syndrome on the venous outflow of the lower limbs and the function of the muscular-venous pump of the lower limbs.

### **Secondary endpoint of the study**

To assess the efficacy and comfort of utilizing compression stockings of class 1 and 2 in the treatment of lower limbs venous outflow disorders and correction of lower limb muscular-venous pump dysfunction in patients with PCS in combination with subclinical and clinically manifested lower limb CVD.

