### **Data processing and statistical analysis**

The data of interest are analyzed using the MS Excel program to create summary tables. Statistical analysis is performed using MS Excel, Statistica 6.0, and the VassarStats online calculator (open source project). The arithmetic mean (M) and standard deviation (SD) were calculated. Qualitative variables are compared using Fisher's exact test, and quantitative variables are compared using Student's criterion or Mann-Whitney U test, as appropriate. Statistical significance was assumed at P value under 0.05.

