### **Publication ethics**

The study results will be published in scientific journals, presented at scientific forums and conferences, and used for creating methodological recommendations by the Ministry of Health. Additionally, information about the study outcomes will be posted on social networks. The leading role in the publications will be played by [name] together with [name], [name], and [name] included as contributors.

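### The compression endpoint is an aim with no deciding measure, its population does not match the enrolled groups, and several efficacy readings share one 0.05 threshold

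*Protocol*

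**What the plan says.** Under the secondary endpoint heading, the protocol sets out this aim: "To assess the efficacy and comfort of utilizing compression stockings of class 1 and 2 in the treatment of lower limbs venous outflow disorders". The calf pump is covered as well, through the stated wish for "correction of lower limb muscular-venous pump dysfunction". The patients meant are those "in patients with PCS in combination with subclinical and clinically manifested lower limb CVD". The endpoint section gives no variable, change from baseline or criterion for success.

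The study description (under the exclusion criteria heading) says how efficacy is to be judged: "Follow-up examinations, including clinical evaluations and radionuclide studies with SPECT of the pelvic veins, are performed 10 days after the initial clinical examination". The compression treatment section likewise relies on repeated clinical and radionuclide examinations after 10 days of wear.

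The statistics section says that "quantitative variables are compared using Student's criterion or Mann-Whitney U test, as appropriate" and that "Statistical significance was assumed at P value under 0.05". It does not single out any efficacy outcome. The publication section says that the results will be "used for creating methodological recommendations by the Ministry of Health".

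**The concern.** Choosing the variable that defines an endpoint is a protocol task. Here the reader is given a domain and a set of repeated examinations, and must choose among several readings after the data are in. One significant change, for example in popliteal transport time in one group, could be presented as evidence that stockings work while other readings stand still or move the opposite way. The 0.05 threshold then no longer describes the chance of a false positive finding on this endpoint.

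The choice of patients is open too, because the population in the endpoint cannot be mapped onto the groups. Since the results are meant to feed national recommendations, it matters which result is the deciding one.

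**Working it through.** **No figure to reproduce.** The protocol gives no power, effect size or family-wise error rate. The only stated figure is the 0.05 level. Sidedness is not stated, so two-sided is assumed.

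**Counting the measures**
- Within the endpoint's own domain (radionuclide venography section): average transport time in the tendon part, the muscle part and the popliteal vein, plus tibial flow rate. That makes 4.
- Also repeated at day 10 as efficacy readings: pelvic-pain and leg-pain VAS (clinical study section), rVCSS (clinical examination section) and the pelvic congestion coefficient (SPECT section). That makes 4 more, so 8 is the upper count.
- Comfort is left out because it has no baseline value.

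**Matching the population to the groups (Study design and study description)**

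| Group | Definition | Fit with the endpoint population |
|---|---|---|
| 1 (n=40) | symptomatic pelvic varices, no symptoms or signs of CVD | fits only if superficial reflux, an inclusion criterion, counts as subclinical CVD |
| 2 (n=40) | CVD with asymptomatic pelvic varices | no pelvic congestion syndrome as the protocol describes it |
| 3 (n=10) | leg varices, no pelvic varices or congestion symptoms | outside |

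No group is defined as congestion syndrome with clinically manifest CVD. At most two groups bear on the endpoint.

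**Chance of at least one significant result if nothing changes**

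For k independent tests at level a, the chance is 1 − (1 − a)^k.
- Any P<0.05, k=4: 1 − 0.95^4 = 0.185.
- Any P<0.05, k=8: 1 − 0.95^8 = 0.337. This covers 4 measures in two groups, or 8 measures in one.
- Favourable direction only (a = 0.025), k=4: 1 − 0.975^4 = 0.096.
- Favourable direction only, k=8: 1 − 0.975^8 = 0.183.

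For correlated measures, normal test statistics were simulated as z_j = √ρ·c + √(1−ρ)·e_j within a group, with groups independent and 300,000 runs. ρ is an assumption. The ρ=0 column is the exact formula.

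| Setting | ρ=0 | 0.3 | 0.5 | 0.8 | 0.9 |
|---|---|---|---|---|---|
| 4 measures, 1 pooled group, any | 18.5% | 17.3% | 15.6% | 11.3% | 9.4% |
| same, favourable only | 9.6% | 8.7% | 7.7% | 5.7% | 4.7% |
| 4 measures, 2 groups, any | 33.7% | 31.8% | 28.7% | 21.4% | 17.8% |
| same, favourable only | 18.3% | 16.7% | 14.9% | 11.1% | 9.1% |
| 8 measures, 1 pooled group, any | 33.7% | 30.1% | 24.9% | 15.7% | 11.9% |

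**Against the nominal level for four measures**
- One pooled group, any: 9.4/5 = 1.9 to 18.5/5 = 3.7 times.
- Two groups, any: 17.8/5 = 3.6 to 33.7/5 = 6.7 times.
- The favourable-only ratios, taken against 2.5%, are similar: 4.7/2.5 = 1.9 to 9.6/2.5 = 3.9 times, and 9.1/2.5 = 3.6 to 18.3/2.5 = 7.3 times.

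**The case against.** **Ranking and adjustment may be in the SAP.** A statistical analysis plan may exist and is not shown, and multiplicity rules commonly sit there. This stands: the absence of an alpha split is not itself a finding. It does not excuse an endpoint with no variable, or a population that the group definitions do not supply.

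**The family is small and its members overlap.** The endpoint is limited to leg outflow and pump function, and the protocol says that transport time varies inversely with volumetric flow, so tibial flow rate may largely repeat the transport times. This also stands. It is why the calculation rests on four measures and runs to a correlation of 0.9. At that extreme, in one pooled group, the favourable-direction error is 4.7%. That is below 5% but still nearly twice its own nominal 2.5%. The eight-measure figure is an upper count, though not an invented one, since the protocol itself lists clinical examination and pelvic SPECT among the efficacy checks.

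**Stronger readings that the protocol does not support.** A reader might infer that the endpoint names no population. It does name one; the trouble is the mismatch. A reader might count eight outcomes in three groups, which gives 57.8% at a correlation of 0.5, but group 3 lies outside the endpoint's population, so that figure does not describe this endpoint. A reader might also infer that one significant result is declared to prove efficacy, or that it would trigger a recommendation. No section says either, and no section sets out a grid of by-group or by-class efficacy tests. The risk comes from the missing rule.

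**Strict error control is much to ask of a secondary endpoint in a cohort study.** That is fair, and it is why labelling the remaining outcomes exploratory is enough.

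**Conclusion.** The point holds in a limited form. The secondary endpoint is an aim over a domain of at least four repeated measures, judged in practice by up to eight, with one common 0.05 threshold and a population that does not correspond to the enrolled groups.

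On the narrow reading of four measures, the chance of at least one P<0.05 with no true change is about 9 to 18.5% in one pooled group and 18 to 34% in two groups. In the favourable direction it is 5 to 10% and 9 to 18%, against 2.5%. Eight measures in one pooled group give 12 to 34%.

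These figures assume two-sided tests, equal correlation between 0.9 and 0, independent groups and no true change from day 0 to day 10. The correlation is not in the protocol, so only the range can be defended. The inflation is moderate, but it is present throughout that range.

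**What to change.** Before any day-10 data are analysed, amend the secondary endpoint and statistics sections as follows:

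- Name one outflow or pump variable as the deciding efficacy measure, for example the day-0-to-day-10 change in average transport time in the muscle part of the leg, tested at two-sided 0.05.
- Name one analysis population, reconciled with the group definitions in the Study design section and the study description. The protocol also differs on who receives stockings: all 90 patients in the Treatments section, but only those with impaired outflow in the study description. The sponsor must reconcile these passages so that the analysis set is clear.
- Report all other outcomes, and all by-group and by-class results, as exploratory estimates with 95% confidence intervals.

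With one test in one population, the chance of any false significant result returns to 5%, or 2.5% in the favourable direction.

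The cost is a few sentences and no extra patients or measurements. The downside is that isolated significant changes in other outcomes can no longer be claimed as proof of efficacy.

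The change controls multiplicity only. With no untreated control, regression to the mean and other changes over time remain, so the day-10 change still cannot be attributed to compression alone.
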